11.1.7. Response Review

All responses will be reviewed by an expert(s) independent of the study at the study's completion.

12. DATA REPORTING / REGULATORY REQUIREMENTS

Adverse event lists, guidelines, and instructions for AE reporting can be found in Section 7.0 (Adverse Events: List and Reporting Requirements).

12.1. Data Reporting

12.1.1. Method

This study will be monitored by the Clinical Data Update System (CDUS) version 3.0. Cumulative CDUS data will be submitted quarterly to CTEP by electronic means. Reports are due January 31, April 30, July 31, and October 31. Instructions for submitting data using the CDUS can be found on the CTEP web site (<http://ctep.cancer.gov>). **Note:** All adverse events that have occurred on the study, including those reported through CTEP-AERS, must be reported via CDUS.

12.1.2. Responsibility for Data Submission

Study participants are responsible for submitting CDUS data and/or data forms to the Coordinating Center quarterly by January 31, April 30, July 31, and October 31 to allow time for Coordinating Center compilation, Principal Investigator review, and timely submission to CTEP (see Section 12.1.1.). For trials monitored by CTMS, the monthly data submission to CTEP from Theradex should be copied to the Coordinating Center

The Coordinating Center is responsible for compiling and submitting CDUS data to CTEP for all participants and for providing the data to the Principal Investigator for review.

12.2. **CTEP Multicenter Guidelines**

This protocol will adhere to the policies and requirements of the CTEP Multicenter Guidelines. The specific responsibilities of the Principal Investigator and the Coordinating Center (Study Coordinator) and the procedures for auditing are presented in Appendix E.

- The Principal Investigator/Coordinating Center is responsible for distributing all IND Action Letters or Safety Reports received from CTEP to all participating institutions for submission to their individual IRBs for action as required.
- Except in very unusual circumstances, each participating institution will order DCTD-supplied agents directly from CTEP. Agents may be ordered by a participating site only after the initial IRB approval for the site has been forwarded by the Coordinating Center to the CTEP PIO ([contact]) except for Group studies.

12.3. **Cooperative Research and Development Agreement (CRADA)/Clinical Trials Agreement (CTA)**

The agent(s) supplied by CTEP, DCTD, NCI used in this protocol is/are provided to the NCI under a Collaborative Agreement (CRADA, CTA, CSA) between the Pharmaceutical Company(ies) (hereinafter referred to as Collaborator(s) and the NCI Division of Cancer Treatment and Diagnosis. Therefore, the following obligations/guidelines, in addition to the provisions in the Intellectual Property

Option to Collaborator ([http:// ctep.cancer.gov/industry](http://ctep.cancer.gov/industry)) contained within the terms of award, apply to the use of the Agent(s) in this study:

1. Agent(s) may not be used for any purpose outside the scope of this protocol, nor can Agent(s) be transferred or licensed to any party not participating in the clinical study. Collaborator(s) data for Agent(s) are confidential and proprietary to Collaborator(s) and shall be maintained as such by the investigators. The protocol documents for studies utilizing investigational Agents contain confidential information and should not be shared or distributed without the permission of the NCI. If a copy of this protocol is requested by a patient or patient's family member participating on the study, the individual should sign a confidentiality agreement. A suitable model agreement can be downloaded from: <http://ctep.cancer.gov>.
2. For a clinical protocol where there is an investigational Agent used in combination with (an)other investigational Agent(s), each the subject of different collaborative agreements, the access to and use of data by each Collaborator shall be as follows (data pertaining to such combination use shall hereinafter be referred to as "Multi-Party Data."
 - a. NCI will provide all Collaborators with prior written notice regarding the existence and nature of any agreements governing their collaboration with NIH, the design of the proposed combination protocol, and the existence of any obligations that would tend to restrict NCI's participation in the proposed combination protocol.
 - b. Each Collaborator shall agree to permit use of the Multi-Party Data from the clinical trial by any other Collaborator solely to the extent necessary to allow said other Collaborator to develop, obtain regulatory approval or commercialize its own investigational Agent.
 - c. Any Collaborator having the right to use the Multi-Party Data from these trials must agree in writing prior to the commencement of the trials that it will use the Multi-Party Data solely for development, regulatory approval, and commercialization of its own investigational Agent.
3. Clinical Trial Data and Results and Raw Data developed under a Collaborative Agreement will be made available exclusively to Collaborator(s), the NCI, and the FDA, as appropriate and unless additional disclosure is required by law or court order. Additionally, all Clinical Data and Results and Raw Data will be collected, used, and disclosed consistent with all applicable federal statutes and regulations for the protection of human subjects including, if applicable, the *Standards for Privacy of Individually Identifiable Health Information* set forth in 45 C.F.R. Part 164.

4. When a Collaborator wishes to initiate a data request, the request should first be sent to the NCI, who will then notify the appropriate investigators (Group Chair for Cooperative Group studies, or PI for other studies) of Collaborator's wish to contact them.
5. Any data provided to Collaborator(s) for Phase 3 studies must be in accordance with the guidelines and policies of the responsible Data Monitoring Committee (DMC), if there is a DMC for this clinical trial.
6. Any manuscripts reporting the results of this clinical trial must be provided to CTEP by the Group office for Cooperative Group studies or by the principal investigator for non-Cooperative Group studies for immediate delivery to Collaborator(s) for advisory review and comment prior to submission for publication. Collaborator(s) will have 30 days from the date of receipt for review. Collaborator shall have the right to request that publication be delayed for up to an additional 30 days in order to ensure that Collaborator's confidential and proprietary data, in addition to Collaborator(s)'s intellectual property rights, are protected. Copies of abstracts must be provided to CTEP for forwarding to Collaborator(s) for courtesy review as soon as possible and preferably at least three (3) days prior to submission, but in any case, prior to presentation at the meeting or publication in the proceedings. Press releases and other media presentations must also be forwarded to CTEP prior to release. Copies of any manuscript, abstract and/or press release/ media presentation should be sent to:

Regulatory Affairs Branch, CTEP, DCTD, NCI
[name]
Bethesda, Maryland 20892
[contact]
Email: [contact]

The Regulatory Affairs Branch will then distribute them to Collaborator(s). No publication, manuscript or other form of public disclosure shall contain any of Collaborators confidential/ proprietary information.

13. STATISTICAL CONSIDERATIONS

13.1. Study Design/Endpoints

13.1.1. Phase I.

The phase I trial will use a 3+3 design with the MTD defined as the highest dose level such that <2 of 6 patients experience dose-limiting toxicity.

13.1.2. Phase II.

There is no standard therapy for differentiated thyroid cancer that is refractory to radioactive iodine. The best studied agent in this disease, doxorubicin, has an estimated response rate of 10%. Although cediranib has not been studied in thyroid cancer, a phase II study of the VEGF inhibitor motesanib diphosphate showed a median progression-free survival (PFS) of 40 weeks. Because we hypothesize that combination therapy will be more effective than single agent treatment, we will randomize in a 1:2 ratio, which should enhance recruitment. The randomization will be stratified by prior therapy with a VEGF-pathway inhibitor (yes vs. no) and performance status (0-1 vs. 2)

The primary endpoint will be PFS, which will be compared between the two treatment arms using a stratified logrank test. To determine the sample size, we noted that the median PFS in 93 patients with radioiodine-resistant thyroid cancer treated with motesanib diphosphate²⁵ was 40 weeks. We therefore assume a median of 40 weeks for the cediranib alone arm. In order to have 85% power to detect a 75% improvement in the median to 70 weeks with combination therapy (hazard ratio [HR]=1.75), 110 patients will be required (36 randomized to cediranib and 74 to cediranib plus lenalidomide), based on a one-sided test at the $\alpha=0.10$ significance level. This calculation assumes 1 year of accrual (9 patients per month) and 1.5 years of additional follow-up for a total study duration of 2.5 years. Kaplan-Meier³⁰ curves will be generated for each treatment arm and the median PFS times estimated using the Brookmeyer and Crowley method³¹. In addition to the logrank test, PFS in the two groups will be analyzed by fitting a Cox³² proportional hazards regression model, adjusting for prior VEGF inhibitor use, performance status, and other baseline risk factors. The goodness of fit of the Cox model and the appropriate functional form for continuous covariates will be assessed using graphical techniques, including inspection of martingale residual plots.

An interim futility analysis will be performed after half of the total number of projected events (40 of 80 projected events). The trial will be stopped for futility if the conditional power at this time point is 15% or less, reducing the power by 2-3%.

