5.1.2. Cediranib and lenalidomide administration

Please note, as of **April 10, 2015**, patients assigned to Arm B (Combination of cediranib and lenalidomide) are to discontinue lenalidomide and may continue on cediranib alone.

After determining the MTD or reaching the maximum dose specified above of cediranib with lenalidomide in the Phase I portion of this study, the Phase II study will be initiated.

Subjects will be randomized in a 1:2 ratio to one of two arms. Randomized stratification will employ prior therapy with a VEGF-pathway inhibitor (yes vs. no) and performance status (0 and 1 vs. 2). In Cohort A, subjects (n = 36) will receive cediranib alone at 30 mg daily. In Cohort B, subjects (n = 74) will receive cediranib and lenalidomide at the dose determined in the Phase I study. Each cycle will be 4 weeks in length. Disease re-evaluation will occur every 8 weeks using RECIST guidelines. After 18 cycles, disease re-evaluation will occur every 16 weeks. Patients without evidence of anti-thyroglobulin antibodies will continue to have thyroglobulin levels measured at each response assessment (usually every 8 weeks). All patients are expected to be on thyroxine suppression therapy and thyroid stimulation hormone (TSH) levels will be monitored pre-therapy and every 8 weeks during therapy.

- Patients will take cediranib or cediranib and lenalidomide. Cediranib will be taken daily at 30 mg. Lenalidomide will be taken on day 1-21 of the 28 day cycle at 15 mg. Proper administration of cediranib and lenalidomide is described in Section 5.1. A 4-week period constitutes one cycle of treatment.
- Patients will be provided with a Medication Diary for cediranib and lenalidomide (Appendix B), instructed in its use, and asked to bring the diary with them to each

appointment. A new copy of the Medication Diary will be given to patients each cycle and for those whose dose is reduced due to adverse events.

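### Does the 15% conditional-power futility rule need amending because the plan names neither the assumed effect nor a post-look critical value?

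*Combined protocol and SAP*

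**What the plan says.** All of this is in Section 13.1.2 (Phase II). The primary analysis: "The primary endpoint will be PFS, which will be compared between the two treatment arms using a stratified logrank test". The size: "110 patients will be required (36 randomized to cediranib and 74 to cediranib plus lenalidomide), based on a one-sided test", at the 0.10 level. The target: "In order to have 85% power to detect a 75% improvement in the median to 70 weeks with combination therapy", which the section writes as a hazard ratio of 1.75, so values above 1 favour the combination.

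The interim plan is two sentences. The first sets the timing: "An interim futility analysis will be performed after half of the total number of projected events (40 of 80 projected events"). The second sets the rule and its cost: "The trial will be stopped for futility if the conditional power at this time point is 15% or less, reducing the power by 2-3" per cent.

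The section does not say which effect conditional power assumes for the second half of the events. It does not label the rule binding or non-binding, and it mentions no adjustment of the final critical value for the look.

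**The concern.** Conditional power is the chance of a significant final result given the interim data and an assumed effect for the remaining data. Without that effect, a 15% cut-off does not fix a boundary. Two statisticians could take the same interim data, one using the design effect and the other the observed trend, and reach opposite decisions.

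The stated cost adds a second doubt. Under the observed trend, a common choice, the loss is about 4 points if the final test stays at 1.2816. It falls to between 2 and 3 points if the rule is binding and the final critical value is relaxed to about 1.19 or 1.20 to bring overall alpha back to 0.10. If such a relaxation had been made without being stated, the final test would run at a nominal one-sided p of 0.115 to 0.117. Continuing past a crossed boundary would then raise type I error to that level. Both the stopping point and the success threshold of the primary comparison would be in question.

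**Working it through.** **Inputs** (Section 13.1.2): one-sided alpha 0.10, so c = 1.2816; design HR 1.75; allocation 36:74 of 110; 80 events at the end and 40 at the look, so the information fraction is t = 0.5.

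**Base design.** Information at 80 events = 80 × (36/110) × (74/110) = 17.61, with square root 4.197. Drift θ = 4.197 × ln 1.75 = 2.349. Power = Φ(2.349 − 1.2816) = 85.7%, against 85% stated. The base design reproduces.

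**Boundary.** For interim statistic Z₁ and assumed drift δ,

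CP = Φ{(Z₁√t + δ(1 − t) − c) / √(1 − t)}.

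CP = 0.15 requires Z₁√t + δ(1 − t) = 1.2816 − 1.0364 × 0.7071 = 0.5487. Hence the boundary b:

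- design HR, δ = 2.349: b = (0.5487 − 1.1743)/0.7071 = −0.885
- observed trend, δ = Z₁/√t: b = 0.5487 × 0.7071 = 0.388
- no effect, δ = 0: b = 0.5487/0.7071 = 0.776
- fixed HR 1.20, δ = 4.197 × ln 1.20 = 0.765: b = 0.235
- fixed HR 1.25, δ = 0.937: b = 0.114
- flat-prior predictive power (variance of the final Z given Z₁ is 1 at t = 0.5): b = (1.2816 − 1.0364) × 0.7071 = 0.173

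The interim HR at the boundary is exp(b/√8.807), where 8.807 is the information at 40 events. Power after the look is P(Z₁ > b, Z₂ > c) with correlation √0.5.

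| Reading, c = 1.2816 | Stop at HR ≤ | Stops if no effect | Stops if HR 1.75 | Power | Loss (points) | Type I error |
|---|---|---|---|---|---|---|
| Design HR 1.75 | 0.74 | 19% | 0.5% | 85.7% | 0.05 | 0.100 |
| Fixed HR 1.25 | 1.04 | 54% | 6% | 83.7% | 2.0 | 0.093 |
| Flat-prior predictive | 1.06 | 57% | 7% | 83.3% | 2.4 | 0.092 |
| Fixed HR 1.20 | 1.08 | 59% | 8% | 82.9% | 2.8 | 0.091 |
| Observed trend | 1.14 | 65% | 10% | 81.5% | 4.2 | 0.087 |
| No effect | 1.30 | 78% | 19% | 75.7% | 10.0 | 0.073 |

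**Observed trend, binding, alpha restored to 0.10.** With b kept at 0.388, c = 1.188 and the loss is 2.7 points. With b recomputed against the new c, b = 0.331 (HR 1.12), c = 1.201 and the loss is 2.3 points. Holding alpha at exactly 0.10 is what singles these values out: under the observed trend, final values from about 1.14 to 1.23 also give 2 to 3 points.

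**Simulation check, observed trend, c = 1.2816.** Two sets of 20,000 trials (exponential PFS, medians 40 and 70 weeks, unstratified logrank) gave power of 87.5% falling to 83.3%, and 87.1% falling to 83.0%. With no effect, rejection under the rule was 9.1% to 9.2%.

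**What the stated cost rules out.** A loss of 2 to 3 points is incompatible with the design-effect reading (0.05) and the no-effect reading (10.0, or 4.4 to 7.4 with a relaxed final value). The readings that remain stop at an interim HR between about 1.04 and 1.14. An interim HR of 1.0 stops the trial under all of them.

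**The case for a change.** The strongest case for a change is that a stopping rule should be computable from the protocol alone, and this one is not. Across the possible assumed effects, the chance of stopping a trial in which lenalidomide adds nothing runs from 19% to 78%. The observed trend at an unadjusted final value also misses the stated cost by more than a point on a like-for-like basis (4.2 against 2 to 3). Two or three added sentences would remove the doubt at no cost in patients.

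The omission of the assumed effect stands, and so does the like-for-like figure of about 4 points for that one reading. The rest does not carry. The full 19% to 78% range includes two readings that the plan's own cost figure excludes. No hidden relaxation of the final test is needed to explain 2 to 3 points, since predictive power or a fixed HR of 1.20 to 1.25 gives it at 1.2816. Simulated power after the unadjusted observed-trend look, 83.0% to 83.3%, is about 2 points below the stated 85%, although the simulated baseline was itself higher (87.1% to 87.5%). The section sets the final test at one-sided 0.10 and uses mandatory wording for the stop. Type I error of 0.115 to 0.117 would need both an adjustment that the text never mentions and a decision to override that wording.

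**Conclusion.** No change to the plan follows. The assumed effect is missing detail: the trial statistician has to choose one to compute conditional power, and the stated cost already limits the choice to rules that behave alike. The plan as written keeps type I error at or below 0.10 and leaves power at 81.5% to 83.7%, close to the implied 82% to 83%. Even if the final critical value had been relaxed to 1.188, the decision would differ in only 1.3% of trials with no effect and 1.5% with HR 1.75. The 2-3% figure cannot be verified uniquely, but it is not shown to be wrong.

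This rests on the normal approximation for the logrank statistic, looks at exactly 40 and 80 events, proportional hazards, and the plain reading that a test specified at one-sided 0.10 uses 1.2816.

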13.2. Sample Size/Accrual Rate

Phase I: 9-18 patients. Accrual 3 patient/mo

Phase II: Sample size 110 patients. Accrual 9-10 patients/mo.

13.3. Stratification Factors

Phase II. Patients will be stratified on prior use of VEGF-pathway inhibitors (yes vs no) and performance status (0 and 1 vs 2).

13.4. Analysis of Secondary Endpoints

13.4.1. Phase I.

The objective response rate of cediranib in combination with lenalidomide in patients with iodine refractory, unresectable DTC who have evidence of disease progression within 6 months of study enrollment will be estimated. In addition, the toxicity, duration of response, progression free survival, and overall survival in patients with DTC treated with cediranib plus lenalidomide will be evaluated.

13.4.2. Phase II.

Overall survival (OS) rates will be estimated and compared between groups using methods similar to that described above for PFS. Response rates will be compared using a chisquare test followed by logistic regression analysis to adjust for covariates.

The percent change in tumor size from baseline to the end of cycle 2 (two months) will be compared between the two groups using a two-sample t test³³. The post-treatment total sum of lengths for a patient with a new lesion will be scored as $1.2 * \max(\text{pre-sum}, \text{post-sum})$ to ensure that the appearance of new lesions corresponds to a disease progression per RECIST criteria. In the event of any early deaths prior to two months, a nonparametric rank sum test will be used in place of the t test, with deaths ranked at the extreme end of the distribution.

Adverse events will be summarized by type and grade. Adverse event rates will be compared between the two treatment groups using a chisquare test for common toxicities and Fisher's exact test for less frequent events.

Repeated measures analysis of variance (RM ANOVA) will be performed to determine the effect of the treatments on serial measurements of TSH and thyroglobulin. It is hypothesized that these levels will decrease over time. Baseline tissue biomarker expression, scored as present or absent, of *B-RAF* and *RAS* mutations will be correlated with response rates using Fisher's exact test, and with PFS and OS by fitting a Cox proportional hazards regression model.

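### Response and early tumour-size change are tested without the randomisation strata, at a small cost in power if those strata predict outcome

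*Combined protocol and SAP*

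**What the plan says.** Section 13.3 states: "Patients will be stratified on prior use of VEGF-pathway inhibitors (yes vs no) and performance status (0 and 1 vs 2"). Section 13.1.2 repeats this for the phase II randomisation. It then carries the strata into the primary analysis of PFS, "which will be compared between the two treatment arms using a stratified logrank test". The supporting Cox model also names both factors: "adjusting for prior VEGF inhibitor use, performance status, and other baseline risk factors". Overall survival is to be handled by methods similar to those for PFS (section 13.4.2).

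Response is handled differently in the same section: "Response rates will be compared using a chisquare test followed by logistic regression analysis to adjust for covariates". The covariates are not listed, and nothing says whether the chi-square or the logistic result is the main one. The percent change in tumour size from baseline to the end of cycle 2 is compared by a two-sample t test, replaced by a rank sum test if any patient dies before two months. No covariate or stratum is mentioned for either.

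The only stated error rate is for PFS, "based on a one-sided test at the $\alpha=0.10$ significance level". Section 13 gives no significance level, power or assumed rate for response or tumour-size change.

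**The concern.** When randomisation is balanced within strata and the strata predict outcome, that balance removes the between-strata part of the variation in the treatment difference. An unstratified test still counts it in its standard error. Its true type I error then falls below nominal and it loses power compared with a test that uses the strata.

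Prior VEGF-pathway inhibitor use is a natural candidate: such patients may enter phase II (section 3.1.4), and both arms receive a VEGFR inhibitor. The documents give no data on whether it predicts response here.

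A second issue needs no assumption about prognosis. With two response analyses planned, no ranking and no covariate list, more than one p-value for response is available in an open-label trial, and the plan does not fix which is quoted.

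**Working it through.** **1. The plan's own figure (PFS).** Inputs from section 13.1.2: HR 1.75, one-sided alpha 0.10, power 85%, "36 randomized to cediranib and 74 to cediranib plus lenalidomide".

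- Schoenfeld events: d = (z₀.₉₀ + z₀.₈₅)² / [a(1−a)(ln HR)²], with a = 36/110. This is 2.318² / (0.2202 × 0.3132) = 77.9, so 78 events against 80 stated.
- Power at 80 events is 85.7%.
- With exponential PFS (medians 40 and 70 weeks), 52 weeks of uniform accrual and 78 of further follow-up, the event probabilities are 0.829 and 0.639. Expected events are 36 × 0.829 + 74 × 0.639 ≈ 77.1, giving power 84.7%.
- 78 events need 110 × 78/77.1 ≈ 111 patients, against 110 stated.

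The PFS design reproduces. There is no corresponding figure for response.

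**2. Inputs for response.** Only the sample size, the 1:2 ratio and the two binary factors (four strata) come from the documents. Everything else is assumed: a common treatment odds ratio (OR) of 2.5, blocks of 3 within strata, and the rates below. Base rate means control-arm response in patients with no prior VEGF inhibitor and performance status 0–1.

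| Case | Prior VEGF / PS 2 prevalence | Base rate | Prognostic OR per factor | Overall control rate | Between-strata share of variance |
|---|---|---|---|---|---|
| None | 30% / 10% | 20% | 1 | 20.0% | 0% |
| Moderate | 30% / 10% | 20% | 0.5 | 16.6% | 1.5% |
| Strong | 30% / 10% | 30% | 0.25 | 22.3% | 6.0% |
| Extreme | 50% / 20% | 40% | 0.1 | 19.2% | 18.8% |

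**3. Tests compared.**

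- Chi-square: z = (p_B − p_A) / √[p(1−p)(1/n_A + 1/n_B)], with p the pooled rate.
- CMH: z = Σ(x_B − n_B·m/n) / √Σ[n_A·n_B·m(n−m) / (n²(n−1))], summed over strata, with m the responders and n the patients in a stratum.

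**4. Results, chi-square → CMH (40,000 simulated trials per case).**

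| Case | Type I error, two-sided 0.05 | Power, two-sided 0.05 | Type I error, one-sided 0.10 | Power, one-sided 0.10 |
|---|---|---|---|---|
| None | 5.1% → 5.0% | 50.6% → 50.2% | 9.9% → 9.9% | 77.2% → 76.8% |
| Moderate | 4.7% → 4.8% | 43.6% → 44.4% | 9.8% → 9.9% | 72.4% → 72.6% |
| Strong | 4.3% → 4.9% | 45.8% → 49.2% | 9.5% → 10.2% | 74.3% → 75.8% |
| Extreme | 3.2% → 5.1% | 27.3% → 38.3% | 7.6% → 9.8% | 58.9% → 66.3% |

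Monte Carlo error is about 0.1 point for two-sided type I error and 0.25 point for power. From unrounded values, the power gain from CMH is −0.4, 0.7, 3.4 and 11 points (two-sided 0.05), or −0.5, 0.2, 1.5 and 7.3 points (one-sided 0.10).

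**5. Cross-check by formula.** If a share s of the null variance lies between strata, the chi-square statistic has standard deviation of about √(1−s). For the strong case, 1.96/√(1−0.0596) = 2.021, a two-sided size of 4.3%. For the extreme case, 1.96/√(1−0.1878) = 2.175, a size of 3.0%. Both agree closely with the simulation.

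**6. Does the planned logistic model recover the loss?** A separate run of 10,000 trials stratified on prior VEGF use only, at one-sided 0.10 and OR 2.5. For control response of 35% (naive) and 10% (pretreated), power was 74.2% for chi-square, 76.4% for CMH and 77.0% for a logistic model containing the factor. For 45% and 5% it was 66.2%, 73.5% and 74.1%. The logistic test's type I error was 10.2% and 10.5%.

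**7. Tumour-size change.** One binary stratum, one-sided 0.10, assumed treatment effect 0.4 SD. With a 1-SD stratum effect, the unadjusted t test has size 7.6% and power 70.4%, against 10.1% and 75.0% with the stratum in the model. With a 0.5-SD stratum effect, power is 73.9% against 75.2%.

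**The case against.** The best reply is that much of the remedy is already in the sentence. The chi-square is followed by a covariate-adjusted logistic regression, nothing ranks the chi-square above it, and the Cox model for PFS names both stratification factors. The natural reading is that the logistic model uses them too, and step 6 shows that it then recovers what CMH recovers. This stands as far as it goes. But the text does not name the covariates or say which result governs, and tumour-size change has no adjusted analysis at all.

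The second reply is that the loss is conditional and usually small. This stands in full. A reader might infer that the unstratified test necessarily costs power. It does not: with non-prognostic strata the two tests are equivalent, chi-square being marginally ahead. The larger losses need very strong prognosis. Control response of 35% against 10% is a prognostic odds ratio of about 4.8, and 45% against 5% is 15.5. At 30% against 18% (odds ratio about 2), power was 79.6% for chi-square and 79.9% for CMH. The documents contain nothing to show which case applies.

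A reader might also infer a risk of false positives, or an error in the stated power. Neither is supported. The error is in the conservative direction, the stated 85% belongs to PFS, and that test is stratified.

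**Conclusion.** The response and tumour-size analyses in section 13.4.2 do not carry through the stratification used in the randomisation and the primary test, and the choice between the two response analyses is left open. This is a minor specification gap in secondary endpoints.

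For response, the loss of power is about 0 points if the strata are non-prognostic or moderately prognostic, about 2 to 3 points if strongly prognostic (1.5 to 3.4 in step 4, depending on the test level), and 7 to 11 points only in the extreme case. A further four-stratum check on other assumed rates (one-sided 0.10, OR 2.5) agrees: 82.2% for both tests with no prognostic effect, 78.2% for both at 0.5 per factor, and 70.8% against 73.0% at 0.25 per factor.

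Every response rate, prevalence and odds ratio is an assumption, and so is the test level, because the plan sets none for these endpoints.

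**What to change.** In section 13.4.2:

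- **Response.** Make the main comparison a CMH test stratified by prior VEGF-pathway inhibitor use (yes/no) and performance status (0–1 vs 2), or name the logistic model containing both factors as the main analysis. State which one governs.
- **Early tumour-size change.** Replace the t test by an ANCOVA containing the same two factors, and use a stratified rank sum test when early deaths occur.

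The cost is a line or two of text. Both factors are already collected at registration (section 4.2), so no data, visits or patients are added. In the step 4 simulations, stratifying on irrelevant factors cost at most about 0.5 point of power.
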